| 10. E | Ethics | 25 |
| 10.1. | Ethics review | 25 |
| 10.2. | Documentation | 25 |
| 11. F | Publication Policy | 25 |
| 12. I | nvestigators | 26 |
| 12.1. | Chief Investigator: | 26 |
| 12.2. | Coordinating Investigator: | 26 |
| 12.3. | Principal Investigators: | 26 |
| 13. F | References | 28 |

1. Preamble

The protocol outlined below is for "The efficacy of adjunctive Garcinia mangostana linn (mangosteen) pericarp for bipolar depression: A 24-Week double-blind, randomised, placebo controlled trial." This trial is to be run at The Melbourne Clinic and Albert Road Clinic in Melbourne, Barwon Health in Geelong and Toowong Specialist Clinic in Brisbane. Data collected from this trial will be collated for analysis and reporting purposes.

2. Introduction

2.1. Overview

Bipolar disorder is a highly debilitating illness often characterized by suboptimal recovery with conventional treatment. While the disorder has two illness phases; mania and depression, it is the depressive phase that dominates the patient's life, confers the greatest burden of disease and is associated with the highest risk of suicide. The depressive phase of the disorder is also more refractory to current therapies, which are generally more efficacious in mania. Thus, multiple agents are often required to achieve an adequate level of recovery.

Bipolar disorder is further characterised by perturbed oxidative biology which include reduction in antioxidants levels (glutathione and glutathione transferase) and a concomitant rise in oxidative stress markers (e.g. malondialdehyde). *Critically, mood stabilising treatments can restore redox balance, and redox active agents such as N-acetylcysteine have antidepressant actions in bipolar disorder.* Similarly, bipolar disorder manifests systemic inflammation and changes in neuroprogressive markers such as Bcl-2, an apoptotic protein, and mitogen-activated protein kinase (MAPK). This current understanding of the pathophysiology of bipolar disorder supports the search for novel therapeutics affecting the pathways of inflammation, oxidative biology, apoptosis and neurogenesis. Buttressed by robust pilot data *we propose to use a readily available, tolerable, natural adjunctive therapeutic for bipolar disorder that targets all the aforementioned pathways.*

Garcinia mangostana Linn, commonly known as mangosteen, is a fruit that grows mainly in South East Asia. The fruit is contained within a husk known as pericarp, containing a multitude of bioactive agents including xanthones, polyphenols, tannins and epicatechins. These components reduce oxidative stress and inflammation and improve neurogenesis, making mangosteen a highly suitable agent to explore as an adjunctive therapy for bipolar depression. Philosophically similar to the proposed study, we initially showed that N-acetylcysteine (also targeting oxidative, inflammatory and neurogenesis pathways) reduced the symptoms of schizophrenia including depression. Subsequently, we capitalised on this, demonstrating N-acetylcysteine's efficacy in bipolar depression, offering further support for the targeting of these pathway. Critically, we have pilot data from a double blind randomised placebo-controlled pilot in 76 participants with schizophrenia, indicating that 180 days of mangosteen (1000 mg/day) is beneficial for the treatment of depressive symptoms, with an effect size of 1.19

2.2.Bipolar Depression

Bipolar disorder (BD) has two illness phases; mania and depression. Individuals with bipolar disorder spend three times longer in the depressive phase of the disorder than the manic phase (1). It is the most lethal phase of the disorder, as it confers substantial suicide risk (2). It is highly disabling, and causes marked occupational and social impairment and reduced quality of life (3). Complicating this, it is the phase of illness where the efficacy of established treatments is weakest.

The three largest modern and most methodologically rigorous trials of antidepressants in bipolar disorder (paroxetine, paroxetine or bupropion and agomelatine) have all been negative (4-6). Antidepressants also confer a documented risk of induction of mania. There is little quality evidence for psychological therapy of acute bipolar depression (7). Lithium, a mood stabiliser, is less useful in depression than in mania, and the evidence for the mood stabiliser valproate in depression is equivocal (8). Some, but not all, atypical antipsychotics demonstrate efficacy in bipolar depression. All of these agents have substantial tolerability issues (9). We have shown that even electroconvulsive therapy (ECT), considered a 'last resort' option for severe or refractory depression, is less effective in bipolar than unipolar (major) depression (10). Thus, the unmet clinical need is greatest in bipolar depression.

2.3.Inflammation, oxidative stress and neurogenesis

Multiple studies have linked BD's pathophysiology with inflammation, and immune dysregulation appears to be a common pathway whereby many of the environmental factors that lead to risk for mood disorders are transduced (11). Immune alterations are associated with symptom severity, acute mood episodes, illness progression, metabolic disturbances, drug effects, increased prevalence of autoimmune and allergic disorders, as well as with neurotrophic alterations in patients (12). Acute episodes are characterized as proinflammatory states based on findings of increased peripheral levels of pro-inflammatory cytokines on depression, such as interleukin (IL)-6 and tumor necrosis factor alpha (TNF- α), and of IL-2, IL-4, IL-6, and TNF- α in mania (13, 14). Moreover, meta-analyses have reported an increase in the levels of TNF- α , soluble TNF receptor type 1, soluble IL-2 receptor, and IL-1 receptor (15). BD can thus be characterized as a systemic inflammatory disease, even though the exact mechanisms by which these alterations take place are not yet known.

The primary antioxidants in the brain, glutathione (GSH), glutathione peroxidase (GPx), catalase (CAT) and superoxide dismutase (SOD) have all been reported to be altered in bipolar disorder (16). In consort, there are consistent findings of increased markers of oxidative stress, the most robust being peroxidation of cellular lipids. Oxidative damage to both proteins (protein carbonylation) and DNA, are also consistently shown (17).

Regarding neurotrophins, serum brain derived neurotrophic factor (BDNF) levels are reduced in individuals with BD during manic and depressive episodes, and its levels have been negatively correlated with the severity of symptoms (18). In addition, symptom remission has been associated with normalization of serum BDNF levels (19), suggesting that this protein may be a marker of illness activity in BD. Lastly, markers of apoptosis such as S100B and caspase-3 activity are increased in bipolar disorder (20).

With research implicating a variety of factors in addition to monoamine abnormalities, such as oxidative stress and markers of neuroprogression (apoptosis and reduced neurogenesis) new therapeutic targets can be identified and ultimately better treatment options provided to people with bipolar depression (21). Our previous trials using adjunctive therapies (N-acetylcysteine) have successfully shown that targeting oxidative stress, inflammation and neurogenesis, in addition to monoamines, is efficacious in treating bipolar depression, providing a mechanistic proof-of-principle of this approach. The translational and implementation framework of the current study is based on the successful model of using N-acetylcysteine as an adjunctive therapy. In this model, we first found that N-acetylcysteine was efficacious in schizophrenia, including in depressive symptoms in that disorder, opening the door to us further proving that it was efficacious in treating depression in bipolar disorder (22).

2.4. Mangosteen (Garcinia Mangostana Linn)

Garcinia mangostana Linn, more commonly referred to as mangosteen, has been used for centuries as a traditional medicine in South East Asia. In recent years mangosteen pericarp and its bioactive compounds have been shown to exert anti-oxidative, anti-inflammatory and neuro-protective effects which are germane to bipolar disorder (23). Pre-clinical studies both *in vitro* and with animals support the therapeutic potential of mangosteen pericarp in bipolar depression. In conjunction with our recent pilot study, trialling mangosteen pericarp in bipolar depression is warranted.

[figure not shown]
Mangosteen pericarp reduces pro-inflammatory cytokines such as IL-6 and TNF-a, to suppress cyclooxygenase and nitric oxide synthase and to attenuate MAPK levels (24). These anti-inflammatory effects of mangosteen pericarp are thought to occur by inhibition of NFκB (25). As outlined, this is congruent with pathway changes in bipolar disorder and the efficacy of anti-inflammatory/oxidant treatment for bipolar depression has been demonstrated in our previous studies with N-acetylcysteine. The anti-oxidative effects of mangosteen pericarp and its bioactive ingredients, mostly polyphenolic derivatives, are also well known. Mangosteen pericarp inhibits lipid peroxidation and glutathione (GSH) depletion, leading to reduced levels of oxidative markers (e.g. malondialdehyde) (26). Mangosteen pericarp provides neuro-protection by scavenging peroxides and peroxynitrite, preventing excito-toxicity-induced oxidative stress, and inhibiting disruption of mitochondrial function (27). Mangosteen pericarp can also affect neuroprotection via modulation of apoptosis. Alterations in neurogenesis in bipolar disorder have been described (21) and therapeutic agents (i.e. mood stabilisers) have been shown to affect these pathways (28).

 α -Mangostin was shown to up-regulate mitogen activated protein kinase (MAPK), extracellular signal-regulated kinases (ERK), Akt, c-Myc/Max and p53 cell signalling pathways. Downstream these pathways affect cell growth, cell proliferation, cell motility, survival, protein synthesis, and transcription via Bcl-2 and p53, two proteins that regulate cell death pathways (29). Lastly, mangosteen pericarp was shown to affect the levels of neurotransmitters and their receptors including acetylcholine, acetylcholine esterase and 5-hydroxytryptamine 2A receptors (30, 31).

The study will use the pericarp of mangosteen, the dark layer between the rind and the flesh (Figure 1). The pericarp contains over 85 bioactive constituents including α - and β -mangostin, with the former being present at the highest concentrations (29, 31). The xanthone constituents, predominantly α -mangostin, are also the most extensively characterised. Xanthones in mangosteen pericarp possess polyphenol derivatives which act as antioxidants (29). Changes in antioxidant levels are well-characterised in bipolar disorder and the efficacy of antioxidant treatment for bipolar depression has been demonstrated in other studies (e.g. N-acetylcysteine). Critically, α -mangostin affects glutathione levels and glutathione peroxidase activity. By targeting antioxidant pathways, mangosteen pericarp may improve symptoms. Interestingly, some xanthones have anticonvulsant properties and it's noteworthy that many mood stabiliser treatments are repurposed anticonvulsants (32).

2.5.Pilot Data

In addition to the preclinical literature indicating mangosteen pericarp has neurobiological activity that could be useful to treat bipolar depression, we also have pilot data to suggest that adjunctive mangosteen pericarp treatment affects mood symptoms. We have just completed a double blind, randomised placebo controlled trial of mangosteen for individuals with schizophrenia (accepted for publication in Molecular Psychiatry). Seventy-six participants took part in the 24-Week treatment trial where 1000 mg/day of mangosteen pericarp (or placebo) was provided to participants who were interviewed over the course of the study to determine changes in symptoms. The study was designed to explore the effects of mangosteen pericarp on symptoms of schizophrenia and significant reductions in positive and negative symptoms

(based on the Positive and Negative Symptoms Scale) were seen. The study also included a validated mood rating scale; the Montgomery Asberg Depression Rating Scale (MADRS). The improvements in depressive symptoms (Figure 1) showed a highly significant clinical effect (Cohen's d=1.19). Indeed, these effects are larger than most trials investigating antidepressant treatment for bipolar depression. Furthermore, there were no reported differences in the

occurrence of adverse events, indicating mangosteen pericarp was safe and well-tolerated.

The pathway from schizophrenia to bipolar disorder in drug discovery is well worn. Many agents such as atypical antipsychotics were discovered this way by our team. Atypical antipsychotics such as olanzapine and risperidone were initially used in schizophrenia and based on our first-in-kind trials, prior to any industry interest, are now a first line treatment for bipolar disorder (33, 34). We also have a track record in first discovering N-acetylcysteine as a beneficial treatment for mood, initially finding that it reduces depression in schizophrenia, then proving efficacy in bipolar disorder. Indeed, overlaps in the neurobiology between bipolar disorder and schizophrenia is concordant with efficacy across disorders. As an exemplar and proof of concept, we have shown that N-acetylcysteine, which shares effects on inflammation, oxidative stress, neurogenesis and apoptosis, reduces symptoms of depression in bipolar disorder and depression. The veracity of this approach is demonstrated by our high-impact trials, highlighted in our May 2015 lead article on pathways to drug discovery in The American Journal of Psychiatry (35). Taken together, the scientific literature and pilot data suggest mangosteen pericarp may be a useful adjunctive treatment for bipolar disorder.

3. Study Objectives/Hypothesis

3.1.Aims/Hypothesis

3.1.1. Aims

The primary aim of this study is to investigate the efficacy of adjunctive mangosteen pericarp 1000mg/day for the treatment of bipolar depression using a 24-Week randomised, placebo-controlled trial. The primary outcome measure will be the change in severity of mood symptoms, measured using the Montgomery Åsberg Depression Rating Scale (MADRS). Secondary outcomes include global psychopathology, substance use, functioning, quality of life, and safety and tolerability data. A follow-up interview will be conducted 4 weeks post-treatment to determine any outcomes following cessation of the trial agent.

3.1.2. Primary Hypothesis

i) 24-Weeks of adjunctive mangosteen pericarp treatment will be superior to placebo in depression, as measured using the MADRS.

3.1.3. Secondary objectives/hypotheses

ii) 24-Weeks of adjunctive mangosteen pericarp treatment will be superior to placebo for reducing symptomology (Clinical Global Improvement for Bipolar Disorder; CGI-BP, Hamilton Anxiety Rating Scale; HAM-A, Bipolar Depression Rating Scale; BDRS, Young Mania Rating Scale; YMRS, Patient Global Impression Scale; PGI), Quality of Life (Quality of life Enjoyment and Satisfaction Questionnaire – Short Form; Q-LES-Q-SF) and functioning (Social and Occupational Functioning Scale; SOFAS, Range of Impaired Functioning Tool; LIFE-RIFT) and cognition (digit span forwards and backwards, trail making and symbol digit test)

- *iii*) Those taking the mangosteen pericarp treatment will have better outcomes 4 weeks post-treatment discontinuation, based on the same symptomology, quality of life and functioning scales (as during the treatment phase) than those taking the placebo
- *iv)* Those taking mangosteen pericarp treatment will have reduced oxidative stress (malondialdehyde) and inflammatory (IL-6, TNF- α and CRP) markers and improved markers of neuroprotection (Bcl-2), in peripheral (blood) samples compared to placebo,
- v) Clinical changes will correlate with discernible changes in oxidative stress markers (malondialdehyde) inflammatory markers (IL-6, TNF- α and CRP) and improved markers of neuroprotection (Bcl-2), in peripheral (blood) samples compared to placebo.
- vi) From both health sector and societal perspectives 24-Weeks of adjunctive mangosteen pericarp treatment will be cost effective compared to placebo where \$50,000 per quality adjusted life year (QALY) is the accepted benchmark for cost-effectiveness in Australia.
- vii) Those taking the mangosteen pericarp treatment will have improved cognition as during the treatment phase) than those taking the placebo

4. Variables and Instruments

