4.4. Efficacy Variables

The primary outcome variable will be the MADRS total score at the end of the 24-week treatment phase.

Secondary outcomes include the Bipolar Depression Rating Scale (BDRS), Young Mania Rating Scale (YMRS) and Hamilton Anxiety Rating Scale (HAM-A) scores. Participant life satisfaction will be rated on the self-reporting scale (Q-LES-Q). Functioning measures will include the Social and Occupational Functioning Assessment Scale (SOFAS), and Longitudinal Interval Follow-Up Evaluation-Range of Impaired Functioning Tool (LIFE-RIFT). The Clinical Global Impressions Bipolar Version (CGI-BP) will be used to rate clinician judgement for improvement and severity of illness. The Patient Global Impression Scale (PGI) will be used to rate participant perception. We will ask participants to complete a number of pen and paper based cognitive tasks; digit span forwards and backwards, trail making and the Symbol Digit task.

In order to undertake a cost-utility analysis (CUA), gains in utility for the participants will be measured in the study. The most common metric developed to measure utility gains from health interventions is the QALY. A QALY is simply calculated by multiplying the period of time spent in a particular health state by the "utility" or preference value assigned to that health state measured on a scale from 0 (denoting death) to 1 (denoting full health). There are different techniques of deriving utility however the simplest is via the use of a multi-attribute utility instrument which is basically a health related quality of life measure (HRQoL) which has pre-determined "weights" assigned to the health states included within the measure – this is called indirect elicitation of utility. We propose to use the AQol4D to assess any utility based HRQoL gains. It comprises four separately scored dimensions, consisting of independent living, relationships, mental health, and senses. It consists of 12 items and takes 2 minutes to complete. The main utility algorithm of the AQoL has been scored using the time trade off method and the questionnaire has sound psychometric properties. The AQoL4D will be administered to study participants at baseline, 12 and 24 weeks. Scoring will be completed with the algorithm provided by the developers of the instrument obtained from: http://www.aqol.com.au/scoring-algorithms.html .

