4.5. Assessment of inclusion and exclusion criteria

4.5.1. Inclusion Criteria

- Aged 18 years or older,
- Have a DSM-V diagnosis of bipolar disorder I or II, or bipolar disorder not elsewhere classified (NEC),
- Currently be in a major depressive episode on SCID-5-RV
- Score at ≥ 20 on the MADRS
- Participants currently under therapy for bipolar disorder will need to have been on that primary therapy for at least four weeks prior to randomization,
- Have the capacity to consent to the study and comply with study procedures,
- Be using effective contraception if female, sexually active and of childbearing age,
- Be able to speak, read, write and understand the English language,
- Participants will be required to nominate a current treating physician and will not be eligible to enter the study until one is identified.
- If a researcher is in doubt at any time about an inclusion criterion point please consult an investigator.
- If the is a delay of >7 days between screening and baseline assessments, or baseline assessment and medication commencement, the inclusion scale (MADRS) should be administered again to ensure the participant still meets eligibility criteria.

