4.9. Exploration of biological correlates

Blood samples will be obtained at baseline and week 24, to be stored and later analysed for biological correlates based on preclinical evidence including markers of antioxidant defence (including antioxidant levels), oxidative stress (including markers of lipid peroxidation and protein carbonylation), and markers of inflammation (including IL1, IL6, CRP and $TNF\alpha$), which interact with oxidative stress.

Table 1: Instruments / procedures to be implemented at each study visit:

| VISIT | 1 | 2 | 3 | 4 | 5 | 6 | 7 | 8 |
|---------------------------------|-----------|------------|------------|------------|------------|------------|---------|-----------------|
| | Baseline/ | Interim | Interim | Interim | Interim | Interim | Primary | Post- |
| | Screening | assessment | assessment | assessment | assessment | assessment | End- | discontinuation |
| | * | | | | | | point | follow-up |
| WEEK | 0 | 4 | 8 | 12 | 16 | 20 | 24 | 28 |
| SCREENING AND CONSENT | | | | | | | | |
| Informed consent | Х | | | | | | | |
| Inclusion/exclusion criteria | X | | | | | | | |
| Demographics | X | | | | | | | |
| Medical history | X | | | | | | | |
| Psychiatric and family history | X | | | | | | | |
| Concomitant medication | X | Χ | Χ | X | X | X | Х | X |
| Pregnancy test (females only)** | X | | | | | | | |
| SCID-5-RV | X | | | | | | | |
| SAFETY | | | | | | | | |
| Adverse Events | X | Χ | Χ | X | X | X | Χ | X |
| EFFICIACY | | | | | | | | |
| MADRS | X | X | Χ | X | X | X | Х | Χ |
| BDRS | Х | Χ | Χ | X | X | X | Χ | Χ |
| YMRS | Х | Χ | Χ | X | X | X | Χ | Χ |
| HAM-A | X | Χ | Χ | X | X | X | Х | X |
| CGI-S | X | X | X | X | X | X | Χ | Χ |
| CGI-I | | Χ | X | X | X | X | Χ | Х |
| PGI | | Χ | Χ | X | X | X | Χ | X |
| COGNITION | | | | | | | | |
| Digit span forwards | X | | | | | | Χ | |
| Digit span backwards | X | | | | | | Χ | |
| Trail making | X | | | | | | Χ | |
| Symbol digit task | X | | | | | | Х | |
| FUNCTIONING AND QUALITY OF LIFE | | | | | | | | |
| Q-LES-Q | Х | X | X | X | X | X | Χ | Χ |
| SOFAS | X | X | Χ | X | X | X | Χ | Χ |
| LIFE-RIFT | X | Χ | Χ | X | X | X | Х | Χ |
| ASSESSMENT OF PREDICTORS AND | | | | | | | | |
| MODERATORS | | | | | | | | |
| SAPAS | Х | | | | | | | |
| DQES V.2 | X | | | | | | | |
| HEALTH ECONOMICS | | | | | | | | |

| VISIT | 1 | 2 | 3 | 4 | 5 | 6 | 7 | 8 |

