9.2. Method of statistical analysis

All analyses will be conducted in accordance with the International Conference on Harmonization E9 statistical principles, and are based on all randomised participants with at least one post-baseline observation (intention to treat population). Reporting of research findings will be done in accordance to CONSORT guidelines. The statistician responsible for the analysis of outcome data will be blind to group allocation. The primary efficacy analysis will assess average treatment group differences for the primary outcome measure MADRS total score over the entire study period and will use a likelihood based mixed-effects model, repeated measures approach (MMRM). The MMRM model includes the fixed, categorical effects of treatment, investigator, visit, and treatment-by-visit interaction, as well as the continuous, fixed covariates of baseline score and baseline score-by-visit interaction. The MMRM includes all available data at each time point and is the preferred method of analyzing clinical trial data in psychiatry as compared to more traditional repeated measures analysis of variance (ANOVA) and analysis of covariance models (ANCOVA). Planned comparisons will be done with the MMRM models to determine between group differences in change of symptoms measures from baseline to week 24. Results from the analysis of dichotomous data will be presented as proportions, with 95% confidence interval, and Fisher's exact p-value where appropriate. Non-parametric statistics will be used when assumptions for parametric methods are violated. Effect sizes will be calculated using Cohen's guidelines. All tests of treatment effects will be conducted using a two-sided alpha level of 0.05 and 95% confidence intervals. Change scores in symptoms and in biological markers will be derived. Pearson Product Moment Correlations will be used to examine the relationships between the change scores for symptoms and the change scores for biological markers in the two groups. Using Fisher's z transformation, we will test whether the correlations obtained for each group are statistically different in terms of strength.

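### YMRS is scored at all eight visits but used only as an efficacy score; treatment-emergent mania or hypomania is not an outcome

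*Protocol*

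**What the plan says.** Entry requires a current depressive episode (Protocol 4.5.1: "Currently be in a major depressive episode on SCID-5-RV") and a MADRS of at least 20.

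The YMRS then has these roles:

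- Section 3.1.3, hypothesis ii, claims superiority over placebo in these terms: "for reducing symptomology (Clinical Global Improvement for Bipolar Disorder; CGI-BP, Hamilton Anxiety Rating Scale; HAM-A, Bipolar Depression Rating Scale; BDRS, Young Mania Rating Scale; YMRS". Hypothesis iii carries the same symptom scales to four weeks after treatment ends.
- Section 4.4 lists it among the efficacy variables: "Secondary outcomes include the Bipolar Depression Rating Scale (BDRS), Young Mania Rating Scale (YMRS) and Hamilton Anxiety Rating Scale (HAM-A) scores".
- Table 1 schedules it at weeks 0, 4, 8, 12, 16, 20, 24 and 28, in the efficacy block. The safety block of that table holds adverse events only.
- Section 9.2 gives the analysis: "Planned comparisons will be done with the MMRM models to determine between group differences in change of symptoms measures from baseline to week 24". All tests of treatment effects there are two-sided at 0.05 with 95% confidence intervals.

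Sections 4.7, 6.13 and 6.14, on safety, mention neither the YMRS nor mania. The background (section 2.2) does name the risk for another class of drug: "Antidepressants also confer a documented risk of induction of mania".

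**The concern.** Where every participant starts depressed, a rise on the mania scale matters at least as much as a fall. The protocol frames the YMRS only in terms of a fall. It does not define a switch, count it or compare it between arms.

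A switch is an event in a few people, and often at only some visits. Averaged over an arm, a few large rises become a small shift in the mean. At stake is whether the report can give a reader the rate of treatment-emergent mania in each arm. The scale that would supply it is already rated throughout, including the post-discontinuation visit.

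**Working it through.** **1. The passages side by side.** Sections 3.1.3 and 4.4 and Table 1 give the YMRS one role, efficacy. Section 9.2 turns that role into a comparison of mean change. Section 9.2 also sets a method for dichotomous data (proportions, 95% CI, Fisher's exact test where appropriate), but no section names a mania or switch outcome for it to be applied to. Section 6.15 shows that the protocol writes a scale-based safety rule where it wants one: it acts on a MADRS suicide item of 5 or 6. The YMRS has no counterpart.

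**2. Inputs for an illustration.** The protocol gives no figure for mania, so there is none to reproduce.

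- From the protocol: N = 120 in the power statement (9.3) and 1:1 allocation (6.6), so 120/2 = 60 per arm; two-sided alpha 0.05 (9.2); six post-baseline visits on treatment.
- Assumed: mean YMRS 4 in non-switchers (gamma, SD 2 to 4); mean 24, SD 5, while manic; any-visit switch rates of 10% v 5% or 15% v 5%; a fraction f of switchers manic at the visit tested. An episode spanning two of the six visits gives f = 1/3, and one spanning a single visit gives f = 1/6.

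**3. What the mean sees.** Mean difference = (difference in switch rates) × (24 − 4) × f.

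- 10% v 5%: 0.05 × 20 = 1.0 point at f = 1; 0.33 at f = 1/3; 0.17 at f = 1/6.
- 15% v 5%: 0.10 × 20 = 2.0 points; 0.67; 0.33.

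**4. Chance of detection.** The mean test is a two-sided t test at one visit, with 20,000 simulated trials per setting. The ranges cover the non-switcher SDs. Fisher's test is by exact enumeration and takes every switch as detected at some visit or as an adverse event.

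| Switch rates | Mean test, f = 1 | f = 1/3 | f = 1/6 | Fisher, any visit |
|---|---|---|---|---|
| 10% v 5% | 13-15% | 6% | 5% | 9% |
| 15% v 5% | 32-39% | 10-12% | 6% | 33% |

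If all switchers are manic at the tested visit, the proportion gains nothing over the mean. It gains when episodes are brief.

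**5. What the proportion would report.** The standard error of the difference is √[p₁(1 − p₁)/60 + p₀(1 − p₀)/60].

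- 9/60 v 3/60: difference 10 points; SE = √(0.002125 + 0.000792) = 0.0540; 95% CI −0.6 to 20.6 points.
- 6/60 v 3/60: difference 5 points; SE = √(0.001500 + 0.000792) = 0.0479; 95% CI −4.4 to 14.4 points.

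These intervals are wide, but they state a rate and how large an excess remains possible. A difference in mean YMRS of a third of a point does neither.

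**The case against.** Four stronger readings are tempting, and the protocol does not support them.

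- *Mania has no planned comparison.* A reader might infer this from the one-directional hypothesis. Section 9.2 plans two-sided between-group comparisons of the symptom measures, so a rise in mean YMRS on active treatment would be tested.
- *Mania surfaces only if the participant volunteers it.* Section 6.13.2.1 also records events seen by staff and events elicited by direct question at each visit. The definition in 6.13.1 covers worsening of an existing condition, and the DSMB reviews adverse events.
- *The YMRS hypothesis cannot be answered because scores start at the floor.* No baseline YMRS is given, and eligibility sets no ceiling on the scale. A benefit could also arise if fewer manic symptoms emerge on active treatment.
- *Switches bias the MADRS result by a known amount.* The primary outcome is "The primary outcome variable will be the MADRS total score at the end of the 24-week treatment phase", and no rule covers scores taken during a switch, so the possibility is open. Its size is pure assumption. With an excess of 5 to 10 percentage points and a MADRS gap of 10 to 15 points, the shift runs from 0.05 × 10 × 1/6 = 0.08 to 0.10 × 15 × 1 = 1.5 points, depending mostly on how many switchers are manic when the MADRS is scored.

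Two further objections have weight. The sentence on induced mania is about antidepressants; the protocol does not class mangosteen as one, and its pilot reported no difference in adverse events. And a cut-off or a sensitivity analysis may properly sit in a statistical analysis plan that is not shown. But the role of the instrument and the list of outcomes are fixed in the protocol, and an analysis plan that added a switch rate would be adding an outcome the protocol does not contain.

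**Conclusion.** The point holds in a limited form. The protocol rates the YMRS at eight visits in participants who all enter depressed, but treats it only as an efficacy score under a hypothesis of reduction. Treatment-emergent mania or hypomania is not an outcome. The planned mean comparison can show worsening, and adverse event recording can pick up episodes, but neither yields a defined rate by arm.

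On the assumptions above, 15% v 5% with brief episodes would be detected by a one-visit mean test in about 6-12% of trials, against 33% for the any-visit proportion. At 10% v 5% both are poor (5-6% against 9%). The one-visit t test is a simplification: the planned baseline-adjusted MMRM could do somewhat better, and an episode falling wholly between visits and unreported would weaken the proportion. The case for change rests on a visible rate with a confidence interval, at little cost. It does not rest on evidence that this agent provokes mania or that the MADRS result is biased.

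**What to change.** Keep the mean YMRS comparison. Add to sections 3.1.3, 4.4 and 4.7 a safety outcome: the proportion in each arm with treatment-emergent mania or hypomania at any post-baseline visit up to week 28. Define it by a pre-stated YMRS cut-off (for example 15, with 12 and 20 as sensitivity values) or a manic or hypomanic adverse event. Say how a participant already at or above the cut-off at baseline is handled, since eligibility sets no ceiling.

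Report it with a 95% CI by the section 9.2 method for dichotomous data, beside the MADRS result, and label it an estimate and not a powered test. A sensitivity analysis of MADRS scores taken while the criterion is met is optional.

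One passage needs reconciling first: section 6.13.2.1 ends adverse event collection with the 24-week intervention period, while Table 1 lists adverse events at week 28. The adverse event part of the definition depends on which applies.

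The cost is wording in three sections, one more table and the choice of a cut-off. No new data are collected.
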